7.0 Expected Risks/Benefits

7.1 Risks

Risks associated with the TMS procedure:

- 1) Seizures: Rare cases have reported the development of seizures during or immediately after magnetic brain stimulation. Individuals who have a history of seizures or have been diagnosed with epilepsy will be excluded from this research study (by thoroughly screening subjects we hope to minimize this risk). Single pulse TMS that we use in this study has been deemed to carry little risk beyond occasionally causing local discomfort. Our stimulation procedures follow published safety guidelines. Seizure activation is extremely unlikely with the single pulse low numbers of stimulation proposed in the current investigation.
- 2) Discomfort: A small number of people find TMS uncomfortable, particularly at high intensities of stimulation. If individuals report feelings of discomfort, stimulation intensity will be reduced or, if not feasible, testing will be terminated.
- 3) Muscle Twitching: Subjects may feel twitches in the muscles of the arm, leg or face during the magnetic stimulation.
- 4) Noise: A loud click during magnetic stimulation may be heard. Subjects will be provided with foam earplugs that can effectively prevent this discomfort.
- 5) Skin Irritation: There is a risk of mild skin irritation at the location where the electrode sensors have been placed, but this usually consists of minor redness that will go away quickly after they are removed.

Risks associated with clinical assessments and balance testing:

- 1) There is a possibility that subjects may lose balance while getting up from sitting or walking or performing the balance test. An authorized research personnel will be present at all times to ensure safety of the subject. A gait belt will be used when the subjects are performing the clinical tests and a safety harness will be used when necessary for balance testing.
- 2) Muscle Soreness or Fatigue: During or following testing subjects may feel temporary muscle aching or general fatigue. Individuals with ALS who are in the treatment group may feel muscle soreness or fatigue associated with training. Risks of both muscle soreness and muscle fatigue will be minimized by terminating training if greater than moderate muscle soreness occurs.

Risks associated with RS-tDCS:

- 1) Discomfort: Subjects may feel tingling or itching when tDCS is being delivered or at the spot where the electrodes are placed. This usually goes away in a minute or so. In a low percentage of people, there is a side effect of nausea or insomnia. If subjects report any symptoms that make the stimulation not tolerable, they can be excused from participating at any time.
- 2) Pain: Participants will be provided a list of standard safety precautions to minimize any risk of harm to themselves or damaging the device. The participants will be informed of typical tDCS side effects such as tingling or itching, which should never be painful. If they feel any pain concentration in one area, they would be asked to abort the stimulation, remove the headband and check the skin for any redness or discoloration. Study personnel would then evaluate if treatment can be continued.
- 3) Light headedness/ phosphene flash: tDCS will automatically stop if the electrode-skin contact is poor. The current intensity will drop to zero, and it is possible that the participant may feel transient light headedness or even see a phosphene flash. Although these symptoms are unusual, they must inform the study personnel so that they can investigate the cause of poor electrode contact.
- 4) Skin redness/burns: The participants will also be instructed not to administer tDCS over skin that is damaged including any cuts, scratches or scars as this could lead to current concentration in that area, causing skin burns. In the event of an accidental application, the participant must notify the study personnel immediately.
- 5) Remaining still: Subjects will need to remain still during the tDCS procedure. The tDCS device must be kept on a flat, secure surface during the stimulation procedure. Subjects will need to avoid any head movements that could jerk the cables or cause the tDCS device to fall on the floor and potentially disconnect the electrodes.
- 6) Worsening of pre-existing medical condition: If the participant notes a worsening of a pre-existing medical condition, such as migraines or balance because of treatment with tDCS, the team must be notified immediately. Although the exact safety plan may be specific to the subject's underlying medical condition, information regarding an emergency contact number and contact details for the nearest clinic/hospital will be provided.
- 7) Feeling anxious: Subjects will be responsible for administering the tDCS procedure themselves so they may feel a little nervous or anxious.
- 8) Device malfunction: tDCS is a low risk procedure and is not expected to cause serious adverse events. To avoid undue risk of tDCS being delivered at a higher intensity, codes will be used to monitor dosage. It is possible that the device may malfunction or have technical issues. In the event of such a problem, subjects will be instructed to switch off the device and inform the research personnel immediately. In addition, as an added safety feature, the device will not work (discharge) unless the electrodes are correctly applied to the scalp and the electrode contact is adequate. The device will prompt subjects to adjust the placement of electrodes, if necessary.

Other Risks:

- 1) Subjects will feel a squeezing sensation on their arm when the cuff is inflated during the blood pressure measurement.
- 2) A risk of this research is a loss of privacy or confidentiality. To minimize this risk, subject study data will be stored and coded. Only authorized research personnel will have access the subject master code and all data.
- 3) Subjects may feel uncomfortable providing personal information in the questionnaires. They will be instructed to skip any questions that they do not wish to answer.

4) Pregnancy testing: Females of childbearing age who test positive during the testing may be surprised or experience distress if they were unaware. If they are not comfortable taking the pregnancy test, they will not be enrolled in the study.

7.2 Benefits

There is no direct benefit to the individual from participating in this research project.

8.0 Data Collection and Management Procedures

The research will be conducted in compliance with state and federal laws, including the Health Insurance Portability and Accountability Act (HIPAA) which require researchers to protect an individual's health information.

Data will be stored and analyzed in the Brain Plasticity Lab located at [name]. To minimize breach of privacy and confidentiality, subject data will be stored and coded. Members of the research team will process the data and it will be stored on computer disks on which the subject's data will be referred to by a participant number that will be assigned based on the date of his/her participation. This will ensure that anyone who views the data will not have access to the subject's personal information. The key to the code, which links the subject's participant number to his/her identity will be stored separate from the data and destroyed ten years after study completion.

The Principal Investigator and the research coordinator will have access to the device key for release of treatment (activation) codes.

The primary investigator and co-investigators will have access to the raw data. The raw data will not be made available to any other individuals. When requested by the subject, we will share the results of the experiments.

Study information from this study may be reviewed by representatives of the study group at University of Illinois at Chicago, the Institutional Review Board (IRB) at the University of Illinois at Chicago, and perhaps, the U.S. Food and Drug Administration (FDA). Study records will be kept confidential to the extent provided by the law. The name of individual subjects or other identifying data will not be used in any report or publication of this study.

9.0 Data Analysis

We will look at pre and post changes in our primary and secondary outcomes measures. A one-way ANOVA will be used to examine changes in adverse events, subject dropouts, and TMS and clinical assessments. A two-way repeated measures ANOVA with groups and time as the two factors will be used to analyze change scores on adverse events, TMS and clinical assessments.

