Before sending the device home, at the training visit, study personnel will complete a tDCS checklist to screen subjects for suitability of RS-tDCS. This will be double checked by the Principal Investigator prior to release of the device to the subject. If the subject qualifies, we will ensure a rigorous training session for the subject and if necessary, the caregiver. We will instruct the subjects to maintain a RS-tDCS log which will be reviewed by staff every 2 weeks until the end of the study. We have many different stops inserted into the protocol for the safety of the participant. The STOP criteria are summarized below:

- tDCS tolerability test – Stop 1: Does not pass tDCS tolerability test, has pain or other adverse effects
- tDCS training visit – Stop 2: Does not understand tDCS
- RS-tDCS sessions:
 - Zoom PHI video call – Stop 3: Three reschedules/ failure to initiate conference
 - Placement of headset: Stop 4: Failure to place headset correctly within 30 minutes at more than one study session
 - Adverse event – Stop 5: Subject reports experiencing any of the critical events
 - Pain- Stop 6: Reporting of a pain score of 7/10 or more at any point
- In addition, a pre-specified interim analysis for the continuation of the entire study will be completed after the first 6 participants complete the study. The adverse events and mean change in ALSFRS-R between the 2 groups will then be compared. The stopping criteria will be defined as a mean difference between groups exceeding 2 standard deviations. If this occurs, the study will be stopped for full review by the medical monitor or revising the protocol before proceeding

[name] will serve as the medical monitor of the study. A DSMB will be established to monitor the study in terms of timely subject enrollment, integrity of data acquisition and storage, and patient safety. There will be three members who will not be a part of the study team, and who will have no conflicts of interest. The DSMB will include a physician, a scientist with clinical trials experience, and a physical or occupational therapist with experience in working with patients with neurological conditions. Adverse events and unanticipated problems will be reported within 24 hours to the IRB and documented on an Adverse Event Log Sheet in the research records.

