12.0 Statistical Considerations

Subjects and their caregivers face difficulties in participating in randomized controlled trials. Some of the issues that limit participation include travel arrangements, travel associated costs, caregiver's time and scheduling of multiple appointments. Hence it is critical to perform a thorough assessment of the potential benefits of RS-tDCS before considering a randomized controlled trial (RCT). We have powered the study to demonstrate safety of RS-tDCS in terms of adverse events. We will study 100 subjects with ALS. For Aim 2, we will be testing 50 subjects per group. For each comparison of 50 subjects with RS-tDCS compared to 50 in the other group, if the true adverse event rates are really equal, we will have 80% power to reject the null of a

higher event rate in the RS-tDCS group. This power will also obtain an estimate of the variance of the treatment effect for use in power calculations for a future study. We have estimated a total of 100 subjects to be included in the study.

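### Section 12 claims 80% power to demonstrate safety by rejecting a higher adverse event rate, but the ANOVAs planned in Section 9 test for a difference and do not have that power

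*Combined protocol and SAP*

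**What the plan says.** Section 12.0 (Statistical Considerations) states the purpose of the sample size: "We have powered the study to demonstrate safety of RS-tDCS in terms of adverse events". The premise, with 50 participants per group, is "if the true adverse event rates are really equal". Under that premise the section claims a power of 80%, and the null to be rejected is a "higher event rate in the RS-tDCS group". This has the form of a one-sided non-inferiority hypothesis. The null is that RS-tDCS is worse, and rejecting it is the evidence of safety. No margin, alpha or event rate is given.

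Section 9.0 (Data Analysis) is a single short paragraph. For adverse events it gives two methods. The first is: "A one-way ANOVA will be used to examine changes in adverse events, subject dropouts, and TMS and clinical assessments". The second is a model with repeated measurements: "A two-way repeated measures ANOVA with groups and time as the two factors will be used to analyze change scores on adverse events". It mentions no confidence limit, shifted null or rule for concluding safety.

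One other between-group comparison of adverse events appears, in Section 11.0 (also in Section 6.0). It is an interim look after the first six completers, with this rule: "The stopping criteria will be defined as a mean difference between groups exceeding 2 standard deviations". Section 11.0 also lists stop criteria for individual participants, a medical monitor and a DSMB.

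**The concern.** The two sections set up opposite hypotheses. Section 12 wants to reject that RS-tDCS has more adverse events. The ANOVAs in Section 9 take equality, or no group-by-time interaction, as the null. Rejecting that null shows that the arms differ. Failing to reject it leaves open both equal rates and a material excess on RS-tDCS.

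Safety is part of Aim 1, so this affects a lead conclusion. If the only final comparison is a difference test, a reader of the results has no planned analysis that can support the claim for which the trial was sized. Loss of participants makes this worse: fewer completers make a non-significant difference more likely. Section 2.0 itself expects higher dropout in progressive disease, and Section 12 states no allowance for it.

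**Working it through.** **Inputs from the documents.** 50 per group, 80% power, true rates equal (Section 12). ANOVAs for adverse events (Section 9).

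**Assumptions, because the documents are silent.** One-sided alpha of 0.05 or 0.025 for the Section 12 test; two-sided 5% for the ANOVA; one yes/no event per participant; sham rate p of 10% to 50%, with 70% as a check.

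**1. The plan's own 80%.** With no margin, a test of the Section 12 null rejects at equal rates only with probability alpha (2.5% or 5%). So 80% needs an unstated positive margin d, where

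d = (z for 1 - alpha + z for 0.80) × sqrt(2p(1 - p)/50).

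At one-sided 5% and p = 0.20: d = (1.645 + 0.842) × sqrt(0.0064) = 2.486 × 0.08 = 0.199.

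| p | Implied margin, one-sided 5% | Implied margin, one-sided 2.5% |
|---|---|---|
| 10% | 14.9 points | 16.8 points |
| 20% | 19.9 | 22.4 |
| 30% | 22.8 | 25.7 |
| 50% | 24.9 | 28.0 |

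The 80% can be reached, but not reproduced uniquely.

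**2. The planned test under the same premise.** At equal rates a two-sided 5% ANOVA is significant about 5% of the time, split about 2.5% each way. Only the half that favours RS-tDCS would reject a higher rate on RS-tDCS. That is about 2.5%, against the stated 80%.

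**3. What non-significance would mean.** Probability that a one-way F test on the 0/1 outcome is non-significant when RS-tDCS is truly worse, with d taken at one-sided 5%:

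| p | Excess = d, 50 per arm | Excess = d/2, 50 per arm | Excess = d, 35 per arm |
|---|---|---|---|
| 10% | 50% | 82% | 62% |
| 20% | 41% | 79% | 55% |
| 30% | 34% | 78% | 52% |
| 50% | 26% | 75% | 42% |

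At p = 70% the full-margin figure with 50 per arm is 14%. With margins from one-sided 2.5%, the full-margin figures at 50 per arm are 41%, 31%, 24% and 16%. Simulation and exact binomial enumeration agree.

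**4. One concrete result.** Take 15/50 events on sham and 20/50 on RS-tDCS. The difference is 10 points and its standard error is sqrt(0.3 × 0.7/50 + 0.4 × 0.6/50) = 0.095. The 95% interval is 10 ± 1.96 × 9.5, or -8.6 to +28.6 points. This is non-significant, yet compatible with a large excess.

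**5. What 50 per arm can deliver.** As estimation, the half-width of a 95% interval at equal rates is 1.96 × sqrt(2p(1 - p)/50): 11.8, 15.7, 18.0 and 19.6 points at p = 10%, 20%, 30% and 50%. As a non-inferiority test with margin m, power at equal rates is Phi(m / sqrt(2p(1 - p)/50) - z for 1 - alpha):

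| Margin | Power over p = 10-50%, one-sided 2.5% | One-sided 5% |
|---|---|---|
| 10 points | 17-39% | 26-51% |
| 15 points | 32-71% | 44-80% |
| 20 points | 52-92% | 64-95% |

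**The case against.** A reader might infer that, followed as written, the plan would declare RS-tDCS safe on a non-significant ANOVA. The documents do not say so. Section 3.0 evaluates safety through the occurrence of adverse events and dropout, Sections 6.0 and 11.0 review safety participant by participant, and a DSMB and medical monitor are in place. This stands. What remains is that none of these is a final between-group test of the Section 12 claim, and the six-completer rule is only a stopping threshold.

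A reader might also infer that the Section 9 tests can never reject the Section 12 null. That is too strong. The null as worded has no margin, so a significant ANOVA in favour of RS-tDCS would reject it. The group contrast from a between-group model would also yield a confidence limit. But at equal rates, the case Section 12 assumes, the favourable result occurs about 2.5% of the time, and no limit or decision rule is specified.

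The miss rates are illustrative. Section 9 speaks of changes and change scores, does not name the one-way factor, and Section 6.0 counts the number of events. Section 2.0 cites common mild effects (tingling 70.6%), so an any-event proportion could be high, and there the miss rate falls (14% at a 70% sham rate). Near ceiling, a non-inferiority limit is not automatically better either. At 90% v 100%, 50 per arm and an assumed 20-point margin, it would pass 62-77% of the time depending on the method, while the ANOVA would miss the difference about 25% of the time.

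Finally, the trial is called a pilot and is meant partly to inform a later study. That lowers the severity but does not reconcile an explicit power claim with a different analysis.

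**Conclusion.** The point holds as a mismatch between sample size and analysis. The stated 80% belongs to a non-inferiority-type test with an unstated margin. The adverse event tests actually planned are significant at equal rates about 5% of the time, and about 2.5% in favour of RS-tDCS. This needs only a two-sided 5% level, and no assumption about the margin.

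It follows that a non-significant ANOVA could not carry a safety claim. How often one would hide a real excess depends on assumptions: 26-50% for an excess equal to the implied margin and 75-82% for half of it, at sham rates of 10-50% with 50 per arm, and less often at higher rates for the full margin. The documents do not support the further step that the sponsor intends to read non-significance as safety; they simply leave the claim without a test.

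This should be fixed, together with the missing margin in Section 12.

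**What to change.** **Section 9.** Replace the two ANOVAs for adverse events with the anodal-minus-sham difference and its confidence interval over weeks 0-12, the only period with a sham control (the delayed-start group then switches to anodal stimulation). Pre-specify an adverse event endpoint that is not expected to be near ceiling, for example the key events of interest named in Section 6.0 or events above a stated severity, rather than any event. State that a non-significant difference will not be read as evidence of safety.

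**Section 12.** Replace the statement that the trial is powered to demonstrate safety, and the 80%, with the precision that 50 per arm gives (half-widths of about 12 to 20 points for rates of 10-50%, before dropout).

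**If the sponsor wants to keep a demonstration of safety.** State a margin with its justification, the one-sided alpha and the assumed event rate. Test it in Section 9 with a one-sided upper confidence limit, and restate the power that 50 per arm delivers for that margin. The margin should not be back-solved from n = 50, which would give about 15 to 25 points at one-sided 5%.

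**Cost.** The estimation route changes wording only, with no new data or participants, but safety becomes an estimate with a fairly wide interval. The testing route is stricter. For margins of 10 to 15 points, power with 50 per arm is below 80% at most event rates. Reaching 80% would take from 50 per arm (15 points, 10% rate, one-sided 5%) to 393 per arm (10 points, 50% rate, one-sided 2.5%).

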As a secondary aim, we will explore the effectiveness of RS-tDCS on upper and lower motor neuron mechanisms in individuals with ALS, quantified using Upper and lower motor neuron mechanisms will be assessed using single-pulse transcranial magnetic stimulation (TMS).

Successful completion of this project will trigger future studies that will test the clinical translation of tDCS as a home-based neuromodulatory adjuvant to slow disease progression in ALS and create a paradigm shift in the clinical management of ALS.

Hence, the objectives of this pilot study are:

- Aim 1: To investigate the safety and feasibility of long-term treatment with anodal RS-tDCS in ALS.
- Aim 2: To determine the effects of 24-weeks of RS-tDCS on disease progression in individuals with ALS, using the ALS Functional Rating Scale (Change in Revised ALS Functioning Rating Scale (ALSFRS-R). Scores range from 0 to 48, with higher scores indicating more function retained.

- Aim 3: To determine the effects of RS-tDCS on upper (UMN) and lower motor neuron (LMN) mechanisms in individuals with ALS, quantified using Upper and lower motor neuron mechanisms will be assessed using single-pulse transcranial magnetic stimulation (TMS).

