4.0 Eligibility

4.1 Inclusion Criteria

The general inclusion criteria will be approximately 100 males and females of any race or ethnic status with the following characteristics:

- Age between 18 – 80 years
- Diagnosis of possible, probable, or definite amyotrophic lateral sclerosis according to El Escorial revised criteria
- Spinal onset ALS with initial weakness in the upper or lower extremity.
- Diagnosed with ALS within the past 5 years
- 1-2 point change in pre-slope of the ALSFRS-R at time of enrollment (ratio of drop in score from 48 to the duration in months from onset of weakness)
- Score ≥ 2 for “swallowing” of the ALSFRS-R
- Score ≥ 2 for “walking” of the ALSFRS-R
- Able to provide informed consent
- Stable dose of riluzole, edaravone, AMX0035 (Relyvrio) or no medications
- Availability of a caregiver for remote administration of tDCS

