6.0 Study Design and Procedures

General Overview

Subjects will attend 1 tDCS tolerability test and training visit, 7-10 testing sessions (2-3 at T0, 2-3 at T1, 2-3 at T2, and 1 follow-up at T3) and 72 remotely supervised tDCS sessions. Testing sessions at four timepoints will involve two to three visits (depending on availability and capacity of the participant). Visit 1: obtain informed consent and administer a pregnancy test, complete the Medical Screening Questionnaire and the TMS and tDCS Safety Questionnaire, measure blood pressure, and perform clinical assessments (1-2 hours). Visit 2: Upper and lower motor neuron mechanisms will be assessed using single-pulse transcranial magnetic stimulation (TMS).

Visit 3: tDCS tolerability testing (30 minutes) will be performed and subjects will be asked to return to the lab with their caregivers for a training session on the use of the Soterix tDCS Mini-CT device (1.5 - 2 hours.). The visits maybe combined if the patient wishes to reduce their travel time. Remotely supervised tDCS sessions are expected to last for 45 minutes which will include up to 20 minutes of stimulation with RS-tDCS and an additional 25 minutes for setting up video conferencing and RS-tDCS equipment. The follow-up testing session will be combined into one visit (up to 4 hours) consisting of the same outcome measures recorded at T0, T1, and T2. If subjects are in the delayed start group, they will receive 24 sessions of sham stimulation followed by 24 sessions of anodal tDCS.

Study Design: Participants will be randomized to receive either sham RS-tDCS (delayed-start control) or facilitatory anodal RS-tDCS (intervention). The intervention group will receive 24 weeks of anodal tDCS (3 times/week; 72 sessions). The delayed-start group will first receive sham tDCS for 12 weeks followed by a switch to anodal tDCS for 12 weeks. Outcome measures will be administered at four time points at entry (T0), at the end of 12 weeks (T1), at the end of 24 weeks (T2) and at a 3-month follow up (T3).

Randomization: Stratified treatment assignment of participants into the two groups will be based on baseline ALFSRS-R score and the pre-slope. Group assignment will be randomized within each category using sequential randomization to achieve study arm balance. Participants and assessors will be masked to the type of stimulation they receive.

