Subjects will report to the Brain Plasticity Lab at UIC located at [name]. All subjects will sign a written informed consent. Females of childbearing age will undergo a urine pregnancy test. Subjects who test positive will not be eligible to participate. Female participants of childbearing age will also be informed that the effects of tDCS on pregnancy are still unknown. If participants of childbearing age are planning to get pregnant or may be pregnant during the 24-week period, they will be instructed to stop the tDCS immediately and will be excluded from the study. All subjects will be asked to complete a medical screening questionnaire and TMS and tDCS safety questionnaires. The medical screening questionnaire will include questions about age, gender, race, medical history, medications and personal habits (such as smoking). The TMS and tDCS safety questionnaire will include questions pertaining to the TMS and tDCS exclusion criteria. Blood pressure will be measured prior to conducting clinical assessments. The first testing visit will last for 1 – 2 hours.

Clinical assessments

Clinical testing will take approximately 60 minutes to complete. The battery of functional measures are listed below, and will include tests of walking and balance. The tests have been validated and are commonly used, non-invasive clinical measures.

- Revised ALS Functional Rating Scale (Change in Revised ALS Functioning Rating Scale (ALSFRS-R). Scores range from 0 to 48, with higher scores indicating more function retained.
91. This will be conducted every two weeks over the phone or Zoom PHI.
- Gait speed will be measured using the average speed over two trials of the 10MWT. Change in Revised ALS Functioning Rating Scale (ALSFRS-R). Scores range from

0 to 48, with higher scores indicating more function retained.

Self-selected and fast walking will be measured as the average walking speed from 2 trials of the 10-m walk test, a reliable and sensitive marker for function in patients with ALS.

- 10-meter walk: The 10-meter walk test (10MWT) is a performance measure used to assess walking speed in meters per second over a short distance. It can be employed to determine functional mobility, gait and vestibular function. We will also employ the use of APDM wearable sensors during the test to assess outcome measures of functional mobility.

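### The planned repeated measures ANOVA names no sphericity correction, covariance structure or strata, so the error rate of the group-by-time test is not controlled

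*Combined protocol and SAP*

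**What the plan says.** Section 9.0 (Data Analysis) gives the method for clinical and TMS outcomes in two sentences. The one that compares arms over time reads "A two-way repeated measures ANOVA with groups and time as the two factors will be used to analyze change scores". It does not mention sphericity, an epsilon correction, a covariance model, covariates or alpha, and it does not say which visits form the time factor.

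The rest comes from other sections:

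- **Visits.** Section 6.0, Study Design: "Outcome measures will be administered at four time points at entry (T0), at the end of 12 weeks (T1"), then "at the end of 24 weeks (T2) and at a 3-month follow up (T3"). Under Clinical assessments, the same section adds of the ALSFRS-R: "This will be conducted every two weeks over the phone or Zoom PHI". It does not say whether those scores enter the ANOVA.
- **Size.** Section 12.0: "For Aim 2, we will be testing 50 subjects per group".
- **Purpose.** Section 1.0, Aim 2: "To determine the effects of 24-weeks of RS-tDCS on disease progression in individuals with ALS, using the ALS Functional Rating Scale".
- **Spread of progression at entry.** Section 4.1: "1-2 point change in pre-slope of the ALSFRS-R at time of enrollment", defined as the drop from 48 divided by months since onset of weakness.
- **Randomization.** Section 6.0: "Stratified treatment assignment of participants into the two groups will be based on baseline ALFSRS-R score and the pre-slope".

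**The concern.** The univariate repeated measures F test for group-by-time is exact only under sphericity, meaning that the difference between any two visits has the same variance. If patients decline at different rates, the difference between T0 and T3 varies more than the difference between T0 and T1, and the condition fails even with complete data. The plan itself expects progression rates to differ: it admits a twofold range of pre-slope and stratifies on it.

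Group-by-time is the term in this ANOVA that shows a different course of decline between arms, so it carries Aim 2. If its level is not controlled, a claim that tDCS changes progression, or a mechanism claim from the TMS measures, does not have the error rate that the p-value implies.

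**Working it through.** The plan gives no figure to reproduce here. It states no type I error, and its one power figure (80%, Section 12.0) concerns adverse event rates.

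**Inputs from the documents.** Visits at 0, 12 and 24 weeks and at a 3-month follow-up; 50 per arm.

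**Assumptions.** T3 at week 37 (24 + 13); nominal level 5%; complete data; independent visit error; individual slope SD of 0.29, 0.5 or 0.8 points a month; visit-error SD of 1 to 3 points. The value 0.29 is the only one tied to the documents: pre-slopes uniform on 1 to 2 and carried forward unchanged have SD 1/√12 = 0.29.

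**Step 1: departure from sphericity.** In months (weeks/4.345) the visits fall at t = 0, 2.76, 5.52 and 8.52. Let r = slope SD / error SD. The F test uses scores centred within patient, so a random intercept cancels. The centred covariance, in units of error variance, has one eigenvalue L = 1 + r² Σ(t − mean t)² and k − 2 eigenvalues equal to 1. The sum of squares is 40.1 for T0 to T3 and 16.6 for T1 to T3. Box's epsilon is

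ε = (L + k − 2)² / [(k − 1)(L² + k − 2)].

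Example, slope SD 0.5 and error SD 1 (r = 0.5):

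- Four visits: L = 1 + 0.25 × 40.1 = 11.0; ε = 13.0² / [3 × (11.0² + 2)] = 0.46.
- T1 to T3 changes: L = 1 + 0.25 × 16.6 = 5.1; ε = 6.1² / [2 × (5.1² + 1)] = 0.69.

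Subtracting each patient's baseline from every visit leaves within-patient contrasts unchanged. Raw scores at four visits and change scores that keep T0 = 0 therefore give the same F. For T1 to T3 changes, the shared baseline error cancels on centring.

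**Step 2: false-positive rate of the uncorrected test.** Reference distributions are F(3, 294) for four visits and F(2, 196) for three. The null distribution was simulated as a ratio of eigenvalue-weighted chi-squares, with no strata effect.

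| Slope SD | Error SD | T0–T3 | T1–T3 changes |
|---|---|---|---|
| 0.29 | 1 | 7.2% | 5.7% |
| 0.29 | 2 | 5.4% | 5.1% |
| 0.29 | 3 | 5.1% | 5.0% |
| 0.5 | 1 | 9.0% | 6.8% |
| 0.5 | 2 | 6.7% | 5.4% |
| 0.8 | 1 | 10.0% | 7.6% |
| 0.8 | 2 | 8.3% | 6.2% |
| 0.8 | 3 | 6.9% | 5.6% |

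**Step 3: ceilings.** The worst case is ε = 1/(k − 1), where F behaves as F(1, 98). The 5% critical values are 2.635 for four visits and 3.042 for three. P(F(1, 98) > 2.635) = 10.8% and P(F(1, 98) > 3.042) = 8.4%. With T1 and T2 changes only, a two-level factor has no sphericity condition, and the size is exactly 5%.

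**Step 4: stratification.** Take four visits, slope SD 0.5, error SD 1 and two balanced pre-slope strata. With the strata omitted from the model, the size is about 9% when pre-slope does not predict later slope, about 8% at a correlation of 0.3, about 7% at 0.5 and just under 1% at 1.0. With the strata and their interaction with visit in the model, it stays between about 7.4% and 9.2%. In a second setting, with pre-slope uniform on 1 to 2 plus extra slope SD of 0 to 0.5 and error SD 1.5 or 2.5, omitting the strata gave 1.7% to 5.8%. Without stratified allocation the range was 4.9% to 8.4%.

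**Step 5: the correction.** With Greenhouse-Geisser degrees of freedom at the true ε and no strata effect, the size is 4.8% to 5.0% in every three- and four-visit case above.

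**Step 6: two-weekly scores.** If all 19 two-weekly ALSFRS-R scores to week 37 entered the ANOVA, the uncorrected size would be about 5% to 18% (slope SD 0.2 to 1.0, error SD 1.5 to 3).

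**The case against.** The strongest case on the other side has four parts.

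- **The spread that the documents support is small.** A pre-slope uniform on 1 to 2 gives at most 7.2% with four visits and 5.7% with T1 to T3 changes, at error SD 1. With two pre-slope strata in the model the within-stratum SD halves to 0.144, and the four-visit size is 5.4%, 5.1% and 5.0% for error SD 1, 1.5 and 2. This stands as a limit on the size. It does not remove the point, because slopes during the trial may vary more than pre-slopes, and nothing in the documents bounds them.
- **The plan analyses change scores.** The natural reading is change at T1 to T3, where 8.4% is the ceiling. This stands, so both readings are reported.
- **Silence is not a commitment to an uncorrected p-value.** This also stands: the fault is that the reported p-value is left open. That still allows the choice between corrected and uncorrected values to be made after the results are seen.
- **This is a pilot with no declared alpha for ALSFRS-R.** That lowers the stakes, but Aim 2 still asks for an effect on progression.

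A reader might go further and infer that the test will run at 7% to 10%. The documents do not support that: it needs four visits in the test and r of about 0.28 to 0.80 a month, and neither SD is given. A reader might also infer that the p-value is always too small, but Step 4 shows that it can be too large once strata are ignored. Nor is the zero variance of a T0 change score a cause, since the F is the same for raw scores.

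**Conclusion.** The concern holds conditionally. As written, Section 9.0 does not fix a group-by-time test that keeps its level when patients decline at different rates. Without a correction and without a strata effect, the size at a nominal 5% is about 5% to 10% for T0 to T3, about 5% to 8% for T1 to T3 changes, and 5% for T1 and T2 changes only. The position in each range depends on slope and visit-error SDs that had to be assumed. With the pre-slope strata left out of the model, the size can fall below 5%, to under 1% in the extreme case. The defensible conclusion is that the error rate is uncontrolled in either direction. It should be corrected before analysis, but it does not put the design itself in doubt.

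**What to change.** For continuous outcomes, replace the two-way ANOVA sentence in Section 9.0 with a likelihood-based repeated measures model that has:

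- group, visit and group-by-visit, with the visits named;
- unstructured covariance across those visits;
- baseline score and the stratification factors (baseline ALSFRS-R and pre-slope), each with its interaction with visit;
- small-sample degrees of freedom.

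State alpha, and say whether the two-weekly ALSFRS-R scores enter the model.

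If ANOVA is kept, include the strata and make the Greenhouse-Geisser corrected p-value the reported one for every within-participant term. The correction alone is not enough: with the strata omitted, it would make an already conservative test more so.

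The cost is one sentence in the plan, standard software and slightly wider intervals. No extra patients, visits or data are needed.
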